Safety will be assessed by all AEs, TEAEs, vital signs, physical examinations, hematology, biochemistry, urinalysis, coagulation parameters, and anti-drug antibodies.

Pharmacokinetics	Plasma samples will be collected for assessment of CSL312 concentrations. From a PK subgroup analysis in CSL312-naïve adult subjects, CSL312 PK parameters (maximum concentration [C_{max}], time to maximum concentration [T_{max}], area under the concentration-time curve from 0-30 days [$AUC_{0-30days}$]) will be derived.
-------------------------	---

Pharmacodynamics	Plasma samples will be collected for assessment of FXIIa-mediated kallikrein activity.
-------------------------	--

Other Assessments	Other assessments to evaluate quality of life and response to treatment will be obtained using the Angioedema Quality of Life (AE-QoL) questionnaire, the Work Productivity and Activity Impairment: General Health (WPAI:GH) questionnaire, the Treatment Satisfaction for Medication Questionnaire version II (TSQM II), and the Subject and Investigator Global Assessment of Response to Treatment (SGART and IGART).
--------------------------	---

Statistical Analyses

A minimum of 100 subjects are planned to receive treatment for a minimum of 12 months. This is a single arm study without a control arm. The sample size for this study is not based on a formal statistical sample size calculation but on the guideline E1A issued by the International Conference on Harmonisation, March 1995. The sample size of 100 subjects allows observation of ≥ 1 AE with a probability of 3% at 95% confidence.

The primary endpoint, TEAEs for all C1-INH HAE subjects receiving CSL312 once monthly, independent of the use of CSL312 200 mg AI or CSL312 200 mg NSD, will be summarized using the Safety Analysis Set, defined as all subjects who receive at least 1 dose of CSL312. The TEAEs will be assessed overall and by the use of CSL312 200 mg AI or CSL312 200 mg NSD. TEAEs are AEs that start on or after the date and time of the first administration of study treatment until the Follow-up Visit. TEAEs with completely or partially missing date or time will be considered treatment-emergent following the worst-case principle, unless the partial date clearly indicates that the AE started before the first administration of study treatment.

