9.1 Definitions

9.1.1 Adverse Event

As per the ICH Topic E2A (Clinical Safety Data Management: Definitions and Standards for Expedited Reporting), an AE is any untoward medical occurrence in a patient or clinical investigation subject administered a pharmaceutical product and which does not necessarily have a causal relationship with this treatment. An AE can, therefore, be any unfavorable and unintended sign (including an abnormal, clinically significant laboratory finding), symptom, or disease temporally associated with the use of a medicinal (investigational) product, whether or not considered related to the medicinal (investigational) product.

The period of observation for AEs extends from the time the subject gives informed consent until the end of study (see [Section 9.4](#) for further details).

AEs may include:

- Exacerbation (ie, an increase in the frequency or severity) of a preexisting condition. Illness present before study entry should be recorded in the medical history section of the CRF and only be reported as an AE if there is an increase in the frequency or severity of the condition during the study.
- A clinical event occurring after consent but before investigational product administration.
- Intercurrent illnesses with an onset after administration of investigational product.

AEs do not include:

- Events identified at screening that meet exclusion criteria.
- Medical or surgical procedures (the condition that leads to the procedure is the AE).
- Situations where an untoward medical occurrence has not taken place. For example:

-
- Planned hospitalizations due to pre-existing conditions, which have not worsened.
 - Hospitalizations that occur for procedures not due to an AE (eg, cosmetic surgery).
 - Hospitalizations for a diagnostic procedure where the hospital stay is less than 24 hours in duration or for normal management procedures (eg, chemotherapy).
 - Overdose of investigational product or any concomitant therapy that does not result in any adverse signs or symptoms.

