9.4 Observation Period for Adverse Events

The observation period for the reporting of AEs (and SAEs) for an individual subject will start at the time of giving written informed consent for participation in the current study and finish upon the subject's final visit.

If the investigator becomes aware of an SAE that has started after the observation period has finished, and there is at least a possible causal relationship with the investigational product or medical device constituent, the event must be reported to the Sponsor following the same timelines and procedures described for SAEs occurring during the study (see [Section 9.6.3](#)).

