9.6 Adverse Event Reporting

9.6.1 Adverse Events

At each clinical evaluation, the investigator (or delegate) will determine whether any AEs have occurred. All AEs are to be recorded in the CRF. If known, the medical diagnosis of an AE should be recorded in preference to the listing of individual signs, laboratory findings, and / or symptoms. The investigator must follow up on the course of an AE until resolution or stabilization. If an AE is ongoing after the end of study visit, the AE will continue to be followed up until resolution, stabilization, or the subject is lost to follow-up.

If, during the study period, a subject presents with a preexisting condition that was not noted at the time of study entry, the condition should be retrospectively recorded in the Medical History CRF.

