10.3.2 Analyses of the Primary Endpoint

The TEAEs for all C1-INH HAE subjects receiving CSL312 once monthly, independent of the use of CSL312 200 mg AI or CSL312 200 mg NSD, will be summarized using the Safety Analysis Set. TEAEs are AEs that start on or after the date and time of the first administration of study treatment. TEAEs occurring until the Follow-up Visit will be summarized. TEAEs with completely or partially missing date or time will be considered treatment-emergent following the worst-case principle, unless the partial date clearly indicates that the AE started before the first administration of study treatment.

TEAEs will be summarized by the number of subjects and percentage of subjects experiencing at least 1 TEAE, the number of events, as well as the event rates per injection and per subject year. TEAEs will be presented for the following:

- All subjects in the Safety Analysis Set (ie, subjects on 200 mg CSL312 once monthly)
- Subjects on 200 mg CSL312 monthly and using CSL312 200 mg AI
- Subjects on 200 mg CSL312 monthly and using CSL312 200 mg NSD

TEAE rates per injection will be calculated as follows:

$$\text{TEAE Rate per Injection} = \frac{\text{Number of TEAE}}{\text{Number of injections}}$$

where number of injections will be the sum of the injections that subjects received during the respective safety evaluation period.

TEAE rates per subject years will be calculated as follows:

$$\text{TEAE Rate per Subject Year} = \frac{\text{Number of TEAE}}{\text{Subject years}}$$

where subject years will be the sum of the time in years that subjects were exposed to study treatment during the respective safety evaluation period.

An overview summary of TEAEs will be provided including:

- TEAE
- SAEs
- Deaths
- TEAEs occurring within 24 hours of investigational product administration
- Related TEAEs
- TEAEs leading to study discontinuation
- TEAEs in each severity category
- TEAEs in each outcome category
- AESIs

A summary table by SOC and PT and an overview summary table of COVID-19 associated TEAEs and a listing showing all COVID-19 associated AEs will be provided.

TEAEs which can be clearly identified to be related to an HAE therapy medication other than CSL312 during the Follow-up Period will be flagged in listings and will be summarized separately.

The overview summary and the summary table by SOC and PT will also be provided for TEAEs occurring while using CSL312 200 mg AI and occurring while using CSL312 200 mg NSD.

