11.2 Adverse Events – Coding and Definitions

TEAEs are AEs which start on or after the date and time of the first administration of study treatment. TEAEs occurring until the Follow-up Visit will be summarized.

Where AE start dates and/or times are missing or partially missing, AEs will be assumed to be treatment-emergent, except if the partial start dates and/or times or the AE end date and/or time indicate that the AE started before the first administration of IP.

Table 4 TEAE Assignment in Case of Missing AE Start Date Elements

Missing elements of AE start	Rule	
Regardless of any missing information for AE start: AE end date / time < first IP start date / time		non-TEAE
Otherwise (ie, if AE end date / time \geq first IP start date / time or AE end date is missing, or AE is ongoing)		
- all		TEAE
- day and month	AE start year \geq IP start year	TEAE
	AE start year < IP start year	non-TEAE
- day	AE start month / year \geq IP start month / year	TEAE
	AE start month / year < IP start month / year	non-TEAE
- time	AE start date \geq IP start date	TEAE
	AE start date < IP start date	non-TEAE

Similarly, for subjects who transitioned to AI, where start dates and/or times of a TEAE are missing will be assumed to be on AI, except if the partial start dates and/or times or the AE end date and/or time indicate that the AE started before first dose with AI. The AI reference date/time will be used instead of the IP start date/time (see [Section 8.2.1](#)).

All reported AEs regardless of when they occurred will be listed.

COVID-19 associated AEs will be identified using the COVID-19 SMQ and will generally be included in TEAE tables identified by their standard MedDRA coding.

If for a TEAE the relationship to study treatment is missing the worst case will be assumed for summarizing analysis (ie, the relationship to study treatment will be assumed to be “Yes”). If the AE or SAE with missing relationship started before the first injection of study treatment it will be considered as “not related” (realistic case). No other imputations for missing AE information will be done.

AEs will be coded using MedDRA. There will be periodic updates of the MedDRA version. The latest licensed version will be used, and version updates will be implemented upon availability. AEs will be primarily classified by MedDRA PT. Analyses will be performed by SOC and PT. Aggregated incidences at SOC level and any TEAE will also be provided.

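### The TEAE definition has no worsening clause, so an AE that began before first dose and worsens or turns serious on CSL312 enters the primary endpoint only if it is recorded as a new AE

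*Protocol*

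**What the plan says.** **Definition.** The Protocol synopsis gives "TEAEs are AEs that start on or after the date and time of the first administration of study treatment until the Follow-up Visit". Protocol 10.3.2, on the primary endpoint, gives "TEAEs are AEs that start on or after the date and time of the first administration of study treatment", and Protocol 10.3.2.1.1 uses the same rule for the secondary safety endpoints. SAP 11.2 gives "TEAEs are AEs which start on or after the date and time of the first administration of study treatment". None of the four mentions an AE that began earlier and later changed in severity or seriousness.

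**Collection.** Under Protocol 9.4 the observation period "will start at the time of giving written informed consent for participation in the current study". Among the things that may be AEs, Protocol 9.1.1 lists "A clinical event occurring after consent but before investigational product administration". Sites record AEs at Screening and at each Run-in contact (Protocol 8.6.2).

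**Worsening.** Protocol 9.1.1 also lists "Exacerbation (ie, an increase in the frequency or severity) of a preexisting condition". It adds that an illness present before study entry goes into medical history and should "only be reported as an AE if there is an increase in the frequency or severity of the condition during the study".

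**Ongoing AEs.** Protocol 9.6.1 says "The investigator must follow up on the course of an AE until resolution or stabilization". That sets how long an AE is followed. It does not say whether a worsening updates the old record or opens a new one.

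**The concern.** A TEAE normally includes an event that was present before treatment and got worse on treatment. Here the start date decides alone, and the documents leave the start date of a worsened, already recorded AE to whoever fills in the form. Two sites could see the same course of events and produce one TEAE and one non-TEAE.

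The trial has a single arm and no hypothesis test, so the descriptive counts and rates are the safety result. No control arm shares the omission. Where it occurs it can only lower the count. It would fall mainly on CSL312-naïve subjects, who have a Screening and Run-in Period in this study and are newly exposed. The overview rows for severity, relatedness and AESIs sit inside the TEAE summary (SAP 11.3), so they depend on the same rule.

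**Working it through.** **1. The plan's own figure.** Protocol 10.1 says 100 subjects allow at least one AE of 3% incidence to be seen with 95% confidence. 1 − 0.97^100 = 0.9524, so the figure reproduces. A worsening clause changes neither this figure nor the sample size.

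**2. The rules applied to four cases.**

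| Case | Governing text | Counted as TEAE? |
|---|---|---|
| AE starts after first dose | All four definitions | Yes |
| Medical-history illness worsens after first dose | Protocol 9.1.1: reportable as an AE on worsening | Yes, if the AE is dated at the worsening |
| Screening or Run-in AE, ongoing at first dose, becomes more severe | 9.1.1 exacerbation text may apply; no rule on opening a new record | Yes if a new record is opened; no if the old one is updated |
| Same, but becomes serious with no rise in frequency or severity | Exacerbation text does not mention seriousness; 9.1.2 and 9.2 treat seriousness and severity as separate attributes | No stated route |

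The last two rows are the gap. SAP Table 4 does not fill it, because it deals only with missing elements of the start date. Its rules are nevertheless built on the same start-date logic.

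There is a side effect. Under SAP 11.2 an AE or SAE with missing relationship that started before the first injection is taken as not related, whereas Protocol 9.3 takes a missing assessment as related. A pre-dose start date can therefore also move an event out of the related counts.

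Roll-over subjects have a parallel case, an AE still ongoing from the lead-in study. SAP 8.4 says an event recorded in this study before their first dose is assigned to no period and only listed. It does not address later worsening.

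**3. Size, as an illustration only.**
- Documented inputs: about 150 subjects enrolled (Protocol 3.5); 36 completers of CSL312_2001 and 64 subjects of CSL312_3001 (Protocol 1.2.3.2). Screening lasts up to 1 month and can share a day with Run-in. Run-in lasts 1 to 2 months, or 3 with Sponsor approval. Pre-dose time is therefore about 1 to 4 months.
- If every possible subject rolled over: 150 − 36 − 64 = 50 naïve subjects. Pre-dose time is 50 × 1/12 = 4.2 to 50 × 4/12 = 16.7 subject-years.
- Assumed, not in the documents: 1 to 3 AEs per subject-year, 25% ongoing at first dose, 10% to 20% of those worsening.
- Low end: 4.2 × 1 × 0.25 × 0.10 = 0.1 events. High end: 16.7 × 3 × 0.25 × 0.20 = 2.5 events. Both scale in proportion to the number of naïve subjects.
- One subject is 1/150 = 0.67%.

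**4. Effect on the plan's figure, also assumed.** Let f be the share of subjects with a 3% event who are missed. P(at least one seen in 100) = 1 − (1 − 0.03(1 − f))^100. This gives 94.5% at f = 5%, 93.5% at f = 10%, 91.2% at f = 20% and 88.0% at f = 30%. The documents give no value for f.

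**The case against.** The strongest reply is that the documents never say a worsened AE keeps its old record. The exacerbation item in Protocol 9.1.1 is worded generally. The restriction to illness before study entry comes in the sentence after it, about medical history. The same section treats a laboratory value already abnormal at screening, hence after consent, as possibly exacerbated. On that reading a worsened Run-in AE is a new AE with a post-dose start and counts. The eCRF and its completion guidance are not among the documents and may already settle the point.

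This stands against two stronger readings that a reader might infer. One is that every pre-dose AE that worsens drops out of the primary endpoint; the documents do not say so, because the outcome depends on an unstated recording convention. The other is that such an event would be hidden in the non-TEAE listing. SAP 11.4 also plans listings of SAEs, AESIs, related AEs and AEs leading to withdrawal or permanent discontinuation of treatment. The SAE table by SOC and PT is not labelled treatment-emergent, so a loss from that table is not established either. SAEs and AESIs are also reported by expedited procedures, and an IDMC reviews safety.

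It does not remove the gap. A reading that sites may adopt is not a rule that they must follow, listings do not feed the primary counts and rates, and the exacerbation text does not cover an AE that only becomes serious.

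**Conclusion.** The point holds in conditional form. All TEAE definitions use the start date alone. An AE begun between consent and first dose that worsens or becomes serious on CSL312 is left out of the primary counts and rates whenever the change is entered on the existing record. It counts if a new record is opened.

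The size is probably small. The range of 0.1 to 2.5 events rests on assumed rates and covers worsening of any degree, so severe or serious cases would be fewer. A reader might infer that CSL312's safety profile is shown to be understated. The documents do not support that: they show an ambiguity that can act in one direction, not a demonstrated loss. The reason to act is that the primary endpoint should not depend on how a site keeps its records, and the remedy is cheap.

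**What to change.** In SAP 11.2, and in the header rule of Table 4, define a TEAE as an AE that starts on or after the first administration, or one that started before it and increases in severity or becomes serious on or after it. Date the second kind at the change and count it at the worsened severity or seriousness. Where a site has already opened a new record for the worsening, count it once.

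Before database lock, use the Planned Analysis Review Meeting (PARM) to go through all AEs ongoing at first dose: Screening and Run-in AEs in CSL312-naïve subjects, and AEs carried over from the lead-in study in roll-over subjects. The SAP already sends unclear TEAE window assignments to that meeting. Record the change in SAP Section 5, since it departs from the Protocol's definition.

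A new instruction to sites would probably come too late. Under Amendment 1, End of Treatment was due no later than September 2025, and SAP version 2.0 is dated 02 Oct 2025. The work is therefore retrospective: a short pre-lock data review, with site queries if the date of change was not captured. TEAE counts may rise slightly.
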